### 7.1 Double-Blind Phase

All efficacy analyses will be conducted in the ITT population. A supportive analysis of the primary and secondary efficacy endpoints also will be conducted in the PP population.

The estimand that is most clinically relevant as well as estimable in a manner that protects the integrity of randomization is the outcome measure (e.g., the percent change in 28-day seizure frequency), where ALL randomized subjects would be included in this analysis throughout the study period. Hence, all available data will be used, even if they were collected after the subject stopped taking study medication, regardless of whether the subject took rescue medication. [Section 7.1.1](#) details the handling of missing data.

For the analyses of seizures, the baseline phase consists of 6 weeks before the first day of treatment and the DB phase starts the day following the first day of DB treatment until the final visit for subjects who do not enter the OLE and up to the day before the first dose of OLE treatment for those who do. The first day of treatment is not in either phase since the seizures could occur both before and after the first treatment.

Tests of significance between the 2 treatment groups will be performed for the primary endpoint with a 2-sided significance level of 0.05.

Seizure diary compliance for the baseline and the post-baseline DB phase intervals will be calculated as:

$100 \times (\text{Number of Days with Available Seizure Diary}) / (\text{Last Available Seizure Diary Date} - \text{First Day of the Phase} + 1)$ .

Seizure diary compliance between visits will be calculated as:

$100 \times (\text{Number of days with available seizure data between visits}) / \text{Number of days between visits}$ , with the days between visits defined as the day of the prior visit up to the day before the current visit.

The compliances will be summarized with descriptive statistics and the percentage of subjects at least 80% compliant.

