### 7.1.1 Handling of Missing Data

The primary analysis will use all available data. Careful educating and monitoring of the study sites will attempt to limit the amount of missing data to nearly zero, but despite these efforts, some missing data may still arise. Thus a sensitivity analysis, in which the missing data will be replaced, will be performed on the primary efficacy endpoint; see [Section 7.1.8](#).

When an item from a secondary or efficacy endpoint is missing, then so will any subscales or totals that include it.

When subjects prematurely discontinue from the study they are asked to complete the non-seizure assessments at the Taper Visit. For analysis purposes, their data from the Taper Visit will be reassigned to the first visit at which the assessment is scheduled subsequent to the discontinuation and the scheduled day is within 32 days of the Taper visit. For example if a subject completed Visit 3 and then prematurely discontinued and completed assessments at the Taper Visit on Study Day 100, then the Taper visit would be reassigned to Visit 5 (Week 17) for analysis purposes since Visit 5 is scheduled for Study Day 120, 20 days after the assessments were actually completed. (Although the first visit after Visit 3 is Visit 4 (Week 9), that visit is scheduled on Study Day 64, which is not within 32 days of Study Day 100.) But if the Taper Visit assessments were completed on Study Day 28 then the Taper visit would not be reassigned to a regular study visit since Study Day 28 is not within the 32-day window of any scheduled visit. Taper Visit assessments that are not reassigned will not be included in the tabulations but will be included in the data listings.

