### 7.1.2 Primary Efficacy Endpoint

The primary efficacy endpoint is the percent change from baseline in 28-day primary seizure frequency during the 17-week DB treatment phase. Primary seizure types include bilateral tonic, generalized tonic-clonic, atonic/drop, bilateral clonic, or focal to bilateral tonic-clonic seizures. Post-baseline 28-day seizure frequency will be calculated as the total number of seizures in the 17-week DB treatment phase divided by the number of days with seizure data in the phase, multiplied by 28. Baseline 28-day seizure frequency will be calculated as the total number of seizures in the baseline phase divided by the number of days with seizure data in the phase,

multiplied by 28. The calculation for percent change from baseline in 28-day seizure frequency will be done as follows for each subject:

$$\left( \frac{[(\text{Post-baseline 28-day seizure frequency}) - (\text{Baseline 28-day seizure frequency})]}{(\text{Baseline 28-day seizure frequency})} \right) \times 100\%$$

The baseline and post-baseline values and the changes and percent changes from baseline in 28-day seizure frequency will be summarized using descriptive statistics.

The difference between the treatment groups in the percent changes from baseline will be tested for statistical significance. Since the percent differences are anticipated to display skewness and/or outliers, the tests will be performed using the Wilcoxon Rank-Sum statistic.

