### **7.1.8 Sensitivity Analyses**

Three sensitivity analyses of the primary efficacy endpoint of change in 28-day frequency of the primary seizure types will be performed:

Intermittent (random/sporadic) missing data during the 17-week DB phase and any missing data during the baseline phase will be assumed missing completely at random and the collected data will be used to calculate the 28-day seizure frequencies. For early drug termination prior to the end of the 17-week DB phase, caregivers will be instructed to continue to provide daily seizure records until the end of the 17-week DB phase (hence further preventing missingness).

In the first sensitivity analysis, the following imputation approach will be used for the primary outcome measure when a subject stops recording measurements permanently (anticipated to be

minimal in occurrence) prior to the end of the 17-week DB phase: for those missing days, the corresponding median PBO data will be imputed (irrespective of treatment arm) as follows:

- Partition the subjects in the PBO arm into quartiles, where the quartile equals  $\text{Floor}[\text{Rank} \cdot 4 / (n + 1)]$ , where  $\text{Floor}[\cdot]$  is the integer floor function, Rank is the rank of the 28-day seizure frequency in the PBO arm based on all available PBO measurements during the 6-week baseline phase (tied scores receive tied ranks), and n is the number of subjects in the PBO arm.
- Assign each subject for whom imputation is needed into the quartile that covers the 28-day seizure frequency based on that subject's available measurements during the 6-week baseline phase. If a frequency is lower than the lower bound of the lowest quartile (which could happen only in the GNX arm), then assign that subject to the lowest frequency quartile; likewise if a frequency is higher than the upper bound of the highest quartile, then assign that subject to the highest frequency quartile. If a frequency falls between two quartiles (which, again, could happen only in the GNX arm), then based on the distances between the frequency and the upper and lower bounds of the lower and higher quartiles, respectively, assign the subject to the closer quartile (in case of a tie, assign to the lower quartile).

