- Within each quartile, compute the median 28-day seizure frequency in the PBO arm based on all available PBO measurements during the 17-week DB treatment phase. Label that 'X', and define 'A' to be  $X/28$ , (i.e., the daily average on placebo during the 17-week DB phase).
- For any days (whether they be on the PBO or GNX arm) with missing counts due to a subject stopping recording measurements permanently, impute 'A' from the corresponding quartile on that day.

The second sensitivity analysis will explore the possibility that subjects who stop recording their seizure counts tend to have higher seizure counts than the other subjects. The imputation method described in the 3rd and 4th bullets above, except that quartiles are not used, will be modified to use the median of the 5 highest counts (equivalent to the 3rd highest count) among all the PBO subjects with data.

The third sensitivity analysis is to examine the effect of GNX compared to PBO among subjects with low Allo-S levels. The open-label phase 2 study 1042-0900 enrolled 30 subjects who were treated for up to six months. In these subjects with various pediatric epilepsies, including 11 with PCDH19 genetic epilepsy and 7 with CDKL5 Deficiency Disorder, Allo-S levels and 28-day seizure rates were assessed. A GNX responder was specified, by post-hoc definition, as having at least a 25% reduction in 28-day seizure rate. In the PCDH19 cohort, responders (n=6) and non-responders (n=5) had plasma Allo-S concentrations of  $501 \pm 430$  pg mL and  $9,829 \pm 6,638$  pg mL, respectively (mean  $\pm$  SD). When performing a retrospective separation of the PCDH19 cohort according to their Allo-S levels, the 7 subjects with Allo-S levels below 2,500 pg mL had a 53.9% reduction in seizure rates while the 4 subjects with Allo-S levels above 2,500 pg mL had a 247% increase.

All 7 of the subjects with CDKL5 Deficiency Disorder in the 1042-0900 study had low Allo-S levels (below 1000 pg/mL), and their median 28-day seizure reduction was 31%.

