## 10. INTERIM ANALYSES AND DATA AND MONITORING COMMITTEE (DMC)

Up to two formal interim analyses are planned, in addition to the final analysis, of treatment effect on the primary endpoint. They will be conducted when 50 subjects and 75 subjects are at least 17 weeks post randomization. The interim analyses will include only those subjects, and will be based on use of O'Brien-Fleming monitoring boundaries regarding benefit and lack of benefit. If the trial is not terminated at the interim analyses, the sample size at the final analysis will be approximately 100 participants.

(Note that while the boundaries discussed in the remainder of this section will be illustrated for the setting in which 50 (75) subjects would be at least 17 weeks post randomization at the interim analysis, these boundaries will be computed based on the actual number 'X' of subjects at the times of the interim analyses.)

In addition, two supportive analyses will be performed, for informational purposes only, at each interim analysis:

- For those subjects who stop recording measurements permanently (anticipated to be minimal in occurrence) prior to the end of the 17-week DB phase, the imputation procedure for the first sensitivity analysis described in [Section 7.1.8](#) will be applied.
- All randomized subjects who are at least 4 weeks post randomization at the time of the interim analyses will be included.

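### Sensitivity analysis 2 imputes the same extreme placebo rate in both arms, so it does not test robustness if clearly more placebo than ganaxolone subjects stop the diary; consider adding a ganaxolone-only scenario

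*SAP*

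**What the plan says.** SAP 7.1.1 sets the base case: "The primary analysis will use all available data". Nothing is imputed there. On the test, SAP 7.1.2 says "the tests will be performed using the Wilcoxon Rank-Sum statistic", applied to percent change, and SAP 7.1 fixes the level: "Tests of significance between the 2 treatment groups will be performed for the primary endpoint with a 2-sided significance level of 0.05".

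SAP 7.1.8 then lists three sensitivity analyses.

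- Analysis 1 fills the days after permanent diary stopping from the placebo arm, by baseline quartile: "the corresponding median PBO data will be imputed (irrespective of treatment arm". Its last step covers both arms: "For any days (whether they be on the PBO or GNX arm) with missing counts due to a subject stopping recording measurements permanently".
- Analysis 2 explores the possibility that "subjects who stop recording their seizure counts tend to have higher seizure counts than the other subjects". It reuses the third and fourth steps of analysis 1 without quartiles, and the method "will be modified to use the median of the 5 highest counts" among placebo subjects with data, that is, the third-highest value. Nothing in the paragraph limits this to one arm.
- Analysis 3 is the low Allo-S subgroup and does not concern missing data.

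Protocol 9.7.7 describes the same three analyses more briefly. Neither document plans a tipping-point, delta-adjusted or other analysis that treats the arms differently. SAP 7.1.8 and SAP 10 both expect few permanent stoppers; SAP 10 introduces them with "For those subjects who stop recording measurements permanently (anticipated to be minimal in occurrence". Neither document gives a rate by arm.

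**The concern.** Analysis 2 is the only planned check on outcomes worse than placebo after diary stopping. The imputed rate is close to the placebo maximum and ignores the subject's own baseline, so most stoppers move to the unfavourable end of the ranking in whichever arm they are. To a large extent the analysis then counts stoppers per arm. If placebo loses clearly more diaries, the imputation pushes placebo down and the comparison shifts toward ganaxolone. A report that analysis 2 agreed with the primary result would then sound reassuring without having tested anything. The split between arms is unknown when the SAP is fixed, so the usefulness of the check depends on which arm happens to lose more diaries.

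**Working it through.** **Design inputs.** SAP 1.3.2 gives 100 subjects randomized 1:1, SD 44.5 for percent change, and one-sided 2.5%. The standard error of the difference is 44.5 × √(2/50) = 8.9.

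- Difference 30: Φ(30/8.9 − 1.96) = Φ(1.41) = 92.1% (plan: 92%).
- Difference 35: Φ(35/8.9 − 1.96) = Φ(1.97) = 97.6% (plan: 97.5%).
- Significance threshold: 1.96 × 8.9 = 17.4 (plan: about 17.5).

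The plan's figures reproduce. They confirm the inputs but do not bear on analysis 2, for which the plan gives no figure.

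**Why the direction follows from the rule.** Take a stopper with baseline b, a share f of double-blind days recorded, and imputed 28-day rate X. The analysed percent change is

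f × (own percent change) + (1 − f) × (X/b − 1) × 100.

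Assume a lognormal baseline with log-SD 1.0. The third-highest of 50 lies near the 48/51 = 94th percentile (z = 1.565), so X is about e^1.565 = 4.8 times the median. A subject at the median baseline with no change of their own and half the days missing scores 0.5 × (4.8 − 1) × 100 = +190%, or 190/44.5 = 4.3 SD above no change. With log-SD 0.6 the ratio is e^(0.6 × 1.565) = 2.6 and the score is +80%, or 1.8 SD. Either way the subject goes to the bad end of the ranking.

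**Simulation, no drug effect.** Assumptions not in the documents: lognormal baseline with median 50 or 54 per 28 days and log-SD 0.7 or 1.0, stopping unrelated to outcome, stop day uniform from 28 to 104 of 118 diary days. There were 50 per arm, percent-change SD 44.5, and 4,000 to 6,000 trials per scenario. The figures are one-sided rejection in favour of ganaxolone (Z > 1.96), as ranges over runs; the primary analysis gives about 2.5%.

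| Stoppers, placebo vs ganaxolone | Analysis 2 |
|---|---|
| 2 vs 1, or 3 vs 2 | 2.7–3.1% |
| 3 vs 1 | 3.6–4.4% |
| 5 vs 2 | 4.6–5.3% |
| 8 vs 2 | 10–12% |
| 7 or 10 stoppers falling at random across arms | 2.1–2.4% |

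At 5 vs 2, giving the high value to ganaxolone stoppers only brings rejection to 1.1–1.6%.

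**Simulation with a real effect.** Here the baseline median is 50, log-SD 1.0, with a floor of 16 per 28 days taken from the inclusion criterion. Between 10% and 90% of days are recorded before stopping, with 1,000 trials per scenario. The entries are mean Z for primary → analysis 2 → ganaxolone-only scenario.

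| Stoppers, placebo/ganaxolone | Difference 0 | Difference 20 | Difference 30 |
|---|---|---|---|
| 10/2 | 0.00 → 1.13 → −0.27 | 2.14 → 2.88 → 1.86 | 3.17 → 3.72 → 2.87 |
| 8/4 | 0.00 → 0.56 → −0.57 | 2.14 → 2.32 → 1.48 | 3.13 → 3.14 → 2.44 |
| 5/5 | 0.03 → 0.03 → −0.67 | 2.17 → 1.85 → 1.34 | 3.13 → 2.67 → 2.22 |
| 2/10 | 0.00 → −1.12 → −1.40 | 2.13 → 0.61 → 0.39 | 3.15 → 1.45 → 1.26 |

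The Monte Carlo standard error of a mean Z is about 1/√1000 = 0.03. With log-SD 0.6 the pattern is the same; for example, 10/2 at difference 20 gives 2.13 → 2.84 → 1.90.

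**The case against.** The case for leaving the analysis alone has real force.

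- **Purpose.** The SAP sets out to explore stoppers in general and does not promise a worst case against ganaxolone. High counts in both arms implement that aim directly. A reader might infer that analysis 2 fails its own purpose; the text does not support that. This point stands.
- **False positives.** A reader might infer that analysis 2 inflates false positives in general. It does not: with stoppers falling at random across arms, rejection is 2.1–2.4%. The higher rates need a fixed excess on placebo. With 10 stoppers split by chance, 8 or more on placebo has probability (45 + 10 + 1)/1024 = 5.5%. This stands, and it makes the point conditional.
- **Likelihood.** A reader might infer that excess placebo stopping is to be expected because lack of efficacy is a listed reason for discontinuation (protocol 4.5.2). Subjects who stop drug in the double-blind phase are asked to keep the diary to its end (protocol 4.5), and if they do, they need no imputation. Placebo subjects who complete the phase go on to open-label ganaxolone, which is a reason to stay. The earlier fragile X trial described in protocol 1.2 had more somnolence on ganaxolone (33.9% vs 5.6%), so stopping could as well go the other way. The documents support neither direction.
- **Consequence.** The primary test does not depend on analysis 2. Analysis 1 already gives ganaxolone stoppers placebo-level counts. At the very low numbers the SAP expects, the shift is small.

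These points remove any claim of a defect in the main analysis. They do not help if clearly more placebo diaries are lost, because no planned analysis would then stress the result against unfavourable outcomes in ganaxolone stoppers beyond placebo level.

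**Conclusion.** The point holds as a cheap improvement to consider. Analysis 2 does what the SAP says, and it stresses the result when stopping is balanced and there is a real effect (5/5 at difference 20: mean Z 2.17 to 1.85), or when more ganaxolone subjects stop. With a clear placebo excess it moves toward ganaxolone: under no effect, from about 2.5% to about 5% at 5 vs 2 and about 10% at 8 vs 2. At 2 vs 1 it is about 3%, and at 8 vs 4 with a difference of 30 it is neutral. In the unfavourable case, agreement between analysis 2 and the primary result is not evidence of robustness.

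The direction follows from the imputation rule. The sizes rest on the assumed baseline distribution, stop times and stopper counts, none of which the documents give, and on reading the imputed value as a 28-day placebo frequency divided by 28, as the inherited steps imply. A reader might go further and want the ganaxolone-only version to replace the present one as the sole criterion. That is a preference, and the documents do not require it.

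**What to change.** In SAP 7.1.8, before unblinding:

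- Keep analysis 2 as written.
- Add one scenario in which only ganaxolone permanent stoppers receive the high-count value and placebo stoppers are imputed as in analysis 1.
- Report both with the number of permanent diary stoppers in each arm.
- State that the both-arm version will not be cited as support for robustness when placebo stoppers outnumber ganaxolone stoppers.

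The cost is one SAP paragraph and one more table. The added scenario is deliberately conservative: in every simulated case with ganaxolone stoppers it put mean Z below the primary analysis. The stated robustness may therefore look less favourable.

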## 7.2 Open-Label Extension

All of the analyses for the DB phase will be repeated for the OLE phase, with the following differences:

- The results will be presented overall and also classified according to the DB treatment received by the subjects
- The post-baseline seizure endpoints will be derived starting from the first dosing day of OLE treatment
- The only sensitivity analysis to be performed is the analysis of the primary endpoint among subjects with low Allo-S levels
- The seizure frequencies during the titration and maintenance phases will not be analyzed separately
- The time points for the efficacy, exploratory, and quality of life endpoints will be at Weeks 21, 34, 52, and every 16 weeks thereafter of open-label treatment relative to the 6-week prospective baseline phase. For the seizure endpoints, this corresponds to the first 4, 17, 35, 51, etc. weeks from the start of the OLE phase
- The differences between the DB treatment groups in the percent changes from baseline of the 28-day seizure frequencies will not be tested for statistical significance
- No PP analyses will be performed
- If a subject prematurely discontinues from the OLE phase, the EEG comparison to baseline at the Final OL/Taper Visit cannot be reassigned for analysis purposes since the EEG is performed only at that visit in the OLE phase; hence the tabulation at that visit will include all the subjects, regardless of whether they discontinued. (Taper Visit assessments among the subjects who prematurely discontinue from the DB phase are reassigned if possible; if they cannot be reassigned then they are not tabulated.)

## 8. PHARMACOKINETICS

A listing of the pharmacokinetic collection times will be provided, but the analyses will be described in a separate report.

## 9. SAFETY ANALYSIS

All safety analyses will be performed in the Safety Population. The results in the DB and OLE phases will be summarized separately. In both phases, the results will be summarized by the DB treatment actually received and, for the OLE phase of the study, combined over the treatment groups.

The number and percentage of days that subjects received study drug, the highest percentage of the maximum allowable daily dose (1800 mg or 63 mg/kg) that subjects received, and the total amount of study drug received will be summarized. The denominator for the percentage of days of study drug is the number of days in the phase. If the subject stops taking drug during the phase then the last day that drug was taken will be used for the last day of the phase, and if the subject is ongoing in the phase then the last known treatment date will be used. For the OLE phase, the number and percentage of days that subjects received study drug will be summarized over just the OLE phase as well as over the entire study (combined DB and OLE phases) but the classification by the DB treatment applies only for the OLE phase summary. The summarization over the entire study will include the DB data only from subjects who were in the GNX group during the DB phase, regardless of whether they entered the OLE, and all the subjects from the OLE phase

A subject data listing will be provided with full details of the study drug dispensation.

Safety assessments include:

- AEs
- Clinical laboratory tests
- Vital signs including temperature, blood pressure, pulse rate, and weight
- 12-lead ECG
- Physical, neurological and developmental examinations
- Tanner staging (OLE phase only)
- Concomitant AED levels

Baseline is defined as the last non-missing value obtained before the first DB treatment.

Assessments performed at multiple post-baseline time points will be summarized at each time point for which they are scheduled, but the listings will also include any assessments performed at unscheduled time points. Assessments performed at the Taper Visit for prematurely discontinued subjects will be reassigned as described in [Section 7.1.1](#); if the assessments are not

reassigned, they will not be included in the tabulations but will be included in the data listings. Subjects who prematurely discontinue from the study are also asked to complete assessments at the Safety Follow-up Post-Taper Visit, but these will not be reassigned.

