7.6. Safety Assessments

Safety will be evaluated by collecting the assessments detailed in the sections below.

Baseline is defined as the last non-missing value obtained before the first double-blind treatment. If any of the baseline safety assessments are outside of normal limits, and the investigator feels is medically significant, the subject may not be randomized. Assessments performed at multiple post-baseline time points will be summarized at each time point for which they are scheduled, but the listings will also include any assessments performed at unscheduled time points.

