## 2. STATISTICAL METHODS

### 2.1 General Considerations

In general, non-categorical variables will be summarized by number of subjects, mean, standard deviation (SD), median, 25th and 75th percentiles, minimum, and maximum values. Categorical variables will be summarized by counts and percentage of subjects in each category.

Except where noted, separate tables and data listings will be prepared for the DB and OLE phases of the study. Only events occurring before entry into the OLE phase will be included in the DB phase outputs, and except where indicated, only pre-treatment events and events occurring after entry into the OLE phase will be included in the OLE phase outputs. The tables for the DB phase will show the results for each DB treatment group, and, where noted, combined over the groups as well. The tables for the OLE phase will show the results for each DB treatment group (all subjects will be receiving GNX in the OLE phase) and combined over them. For the efficacy endpoints, the results will be derived according to the randomized treatment group; for the other endpoints, they will be derived according to the treatment actually received.

Source data for the summary tables and statistical analyses will be presented as subject data listings, which include data collected on the electronic case report forms (eCRFs) as well as any derived efficacy variables for all enrolled subjects.

Baseline seizure activity will be determined by 6 weeks of prospective recording in subject daily seizure calendars, which are provided after signing informed consent. Within the DB phase of the study, post-baseline seizure activity will be determined by the days following the first day after the first DB treatment. (The first day of DB treatment is included in neither the baseline nor DB phase since seizures could occur both before and after the initiation of treatment.) Within the OLE phase, post-baseline seizure activity will be determined by the first day of OLE treatment.

Baselines for non-seizure efficacy and safety assessments are defined as the last non-missing value of the assessment before the first dose of treatment.

The OLE phase will use the same baseline as the DB phase.

The study day for all assessments that are performed on or after the first day of treatment will be calculated as:

Study Day = date of the assessment – date of first treatment + 1.

For assessments performed before the first day of treatment, the study day calculation is:

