## 9.1 Adverse Events

Adverse events (AEs) will be coded by System Organ Class (SOC) and Preferred Term (PT) using the MedDRA®, version 16.0 or higher. The verbatim term will be included in the AE listings. Except where indicated, the summary tables will include only TEAEs. All AEs, treatment-emergent or otherwise, will be presented in subject data listings.

A treatment-emergent adverse event (TEAE) is defined as an AE that starts or worsens on or after the first dosing day of study drug. The AE analyses for the main 17-week DB treatment phase of the study will include AEs that start or worsen during that phase and will not include AEs that start or worsen during the OLE phase; ie, they will not include any AEs starting or worsening on or after the first dosing day of the OLE phase.

For the OLE phase of the study, the AEs will be summarized over just the OLE phase as well as over the entire study (combined DB and OLE phases) but the classification by the DB treatment applies only for the OLE phase summary. The summarization over the entire study will include AEs in the DB phase only from subjects who were in the GNX group during the DB phase, regardless of whether they entered the OLE, and all the subjects from the OLE phase; i.e., it will include only the AEs following GNX exposure. The summarizations over just the OLE phase will include TEAEs that start or worsen after the first day of the OLE phase; the summarizations over the entire study will include TEAEs that start or worsen on or after the first dosing day of GNX.

The TEAEs will be summarized as the number of events and the number and percentage of subjects with TEAEs. Subjects who report the same PT on multiple occasions will be counted once for the PT: under the highest severity (severe > moderate > mild) when summarized by severity and under the closest relationship (related > unrelated) to study drug when summarized by relationship. TEAEs with missing relationships will be considered as related.

If a subject reports multiple PTs for a SOC, the subject will be counted only once for that SOC. For the counting of events, all the PTs will be included in the counts, even when subjects have multiple PTs.

Pre-treatment emergent AEs by will be summarized by SOC and PT (only for the DB period summary).

TEAEs will be summarized as below.

- An overview table of TEAEs, including number of events and number (%) of subjects with
  - TEAEs

- serious TEAEs (Treatment-emergent SAEs)

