**9.3.2 ECG**

The 12-lead ECG parameters including value and change from baseline will be summarized using descriptive statistics by baseline and post-baseline visit. Except for QTc, the parameters will be assigned an LNH classification according to whether the value was below (L), within (N), or above (H) the normal reference range. Values outside the normal range, and the QTc parameters, will also be classified as to whether they were potentially clinically significant (PCS).

ECG normal ranges and PCS criteria are:

**HR:** Same as in Vital Signs  
**PR interval:** PCS: < 0.9xLLN or >1.1 x ULN  
**QRS:** PCS: >1.1x ULN  
**QTc B/FN interval:** PCS: ≥ 470 msec (females), ≥ 450 msec (males), or increase ≥ 60 msec from baseline

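### For subjects randomised to placebo, open-label laboratory, vital-sign and ECG changes are measured from before the placebo phase, so these tables mix up to 17 placebo weeks into results shown under GNX

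*SAP*

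**What the plan says.** The safety baseline is defined in three places, and they agree. Protocol 7.6: "Baseline is defined as the last non-missing value obtained before the first double-blind treatment". SAP 2.1: "Baselines for non-seizure efficacy and safety assessments are defined as the last non-missing value of the assessment before the first dose of treatment". SAP 9: "Baseline is defined as the last non-missing value obtained before the first DB treatment". The sentence that settles the open-label phase is in SAP 2.1: "The OLE phase will use the same baseline as the DB phase".

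On the tables, SAP 9 says: "The results in the DB and OLE phases will be summarized separately". The open-label tables are split by double-blind group and also combined, and SAP 2.1 notes of them that "all subjects will be receiving GNX in the OLE phase".

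Change from baseline by visit is planned for laboratory tests (SAP 9.2), vital signs (9.3.1) and ECG (9.3.2). Baseline-by-visit shift tables are planned for the laboratory low/normal/high classes and for the overall ECG interpretation. Some PCS criteria also refer back to baseline, such as the QTc criterion "or increase ≥ 60 msec from baseline".

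Adverse events are treated differently. For the entire-study summary, SAP 9.1 says "it will include only the AEs following GNX exposure".

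**The concern.** In the GNX arm the pre-double-blind value is also the last value before GNX, so one baseline serves both phases. In the placebo arm it is not: GNX starts at the end of Visit 5 (Week 17), after a placebo phase of up to 17 weeks. An open-label change in such a subject is the sum of what happened on placebo and what happened on GNX, and it is printed in a table where everyone is on GNX.

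The distortion can go either way. Drift on placebo can be read as a GNX effect, and recovery on placebo can cancel a later worsening on GNX. SAP 1.2.5 plans an analysis of the open-label data up to a cutoff for the NDA submission, so these tables will be read as part of the long-term safety record. The SAP already ties the entire-study adverse-event and exposure summaries to GNX exposure; laboratory, vital-sign and ECG results have no matching rule.

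**Working it through.** The plan gives no figure to reproduce. The check is a reading of the definitions, a calculation of elapsed time, and an illustration under assumed parameters.

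**Inputs.** Planned sample 100, randomised 1:1 (Protocol 9.5), so about 100 × 1/2 = 50 placebo subjects. Longest placebo period 17 weeks (Protocol 6.2.2). Open-label visits at Weeks 21, 34 and 52 (schedules of assessments). GNX starts at the end of Visit 5, Week 17 (Protocol 6.2.3).

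**1. Share of the baseline-to-visit interval spent on placebo** = 17 / week of visit.

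| Visit | Current baseline | Last pre-GNX value: weeks covered |
|---|---|---|
| Week 21 | 17/21 = 81% | 21 − 17 = 4, none on placebo |
| Week 34 | 17/34 = 50% | 34 − 17 = 17, none on placebo |
| Week 52 | 17/52 = 33% | 52 − 17 = 35, none on placebo |

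Nothing changes for subjects randomised to GNX.

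**2. Which outputs depend on baseline.**

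- Affected: change from baseline for laboratory, vital signs and ECG; the laboratory class and ECG-interpretation shift tables; the QTc increase flag; the blood pressure and pulse criteria that apply when the baseline value was clinically significant; the urinalysis criteria that compare with the pre-treatment result, read with the SAP's baseline.
- Not affected: the low/normal/high class at a visit; PCS limits expressed as multiples of the normal range or as an absolute QTc; adverse-event tables; all double-blind tables; efficacy.

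**3. Two placebo subjects under the current rule (ALT).**

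| Pre-double-blind | Week 17 (placebo) | Week 21 (GNX) | Open-label table | Change on GNX |
|---|---|---|---|---|
| Normal | High | High | Normal to high | None |
| High | Normal | High | No shift | Normal to high |

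**4. Data available.** Visit 5 includes vital signs with weight, ECG, laboratory tests and urinalysis (Protocol 7.2.3). Height is not taken there (Protocol 7.6.2).

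**5. Illustration only.** Every parameter here is assumed: a normally distributed measurement with no drug effect, between-subject SD 1, a slow within-subject component with SD 0.8 and 17-week correlation 0.3 to 0.5, visit noise SD 0.3 to 0.5, and an upper limit at the 97.5th percentile. Of the Week 21 normal-to-high shifts, about 35% to 48% were already high at Week 17. As a share of all subjects that is about 0.64% to 0.77%. Among 50 subjects: 50 × 0.0064 = 0.32 and 50 × 0.0077 = 0.39, so about 0.3 to 0.4 of a subject per parameter.

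**The case against.** The strongest reply is that this is a deliberate and consistent choice. Protocol and SAP agree on one drug-free baseline, which keeps both groups on one scale across phases. The placebo-to-GNX group has its own open-label column, and the double-blind tables show the same group's Week 17 values against the same baseline, so group-level drift can be seen. Subject-level values are listed. SAP 1.2.5 warns that open-label results need caution because there is no control group. Clinically significant laboratory, vital-sign or ECG changes may also be recorded as adverse events (Protocol 8.1.5), which are handled separately. The effect of starting GNX is best judged in the randomised phase.

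Much of this stands. It limits the point to subject-level changes, shift cross-tabulations and baseline-relative flags, and to the combined column. It does not remove it: marginal tables at two visits cannot show which subjects moved between them, and the combined column cannot be separated at all. Nor is it only a matter of taste, since the SAP follows the GNX-exposure principle elsewhere.

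A reader might infer more than the documents support:

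- That 81% of a Week 21 change is bias. The figure measures time; a stable parameter would show no bias.
- That several subjects will be misclassified. The documents give no rate of lasting shifts on placebo from which to derive a count.
- That all open-label safety output is affected. Most PCS limits are absolute, and no vital-sign shift table is planned.
- That a new baseline would also cure unequal exposure in the combined column. At Week 34 the double-blind GNX subjects have had 34 weeks of GNX and the placebo subjects 34 − 17 = 17, whichever baseline is used.
- That the SAP itself attributes open-label shifts to GNX. It makes no such statement; the risk lies in how the tables will be read.

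**Conclusion.** The point holds, in a limited form. As written, the open-label change, shift and baseline-relative PCS summaries for about 50 placebo subjects include up to 17 weeks on placebo. A shift that arose on placebo can be displayed under GNX, and a change after GNX starts can be masked. This rests on the text and on the nominal visit schedule, and on placebo subjects entering the open-label phase; fewer entrants would mean fewer affected.

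The likely size is small for any one parameter: a fraction of a subject at Week 21 under the assumed illustration, with the true figure unknown. No double-blind safety or efficacy conclusion is at risk. It is a worthwhile, inexpensive improvement to descriptive tables, not a flaw in the trial.

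**What to change.** In SAP 2.1 and 9, state that for open-label laboratory, vital-sign and ECG change, shift and baseline-relative PCS summaries, baseline is the last non-missing value before the first dose of GNX. That is:

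- the pre-double-blind value for subjects randomised to GNX;
- the Visit 5 value, or the last one before open-label dosing, for subjects randomised to placebo;
- the screening value for height, which Visit 5 does not measure.

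Build the combined column on the same per-subject baseline, and say that the urinalysis pre-treatment comparison follows it. Keep the pre-double-blind baseline for double-blind tables and for efficacy in both phases. The current open-label display can stay as a secondary table if the single scale is wanted.

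Cost: a short addition to the SAP and one derived variable, with no new data. The drawback is two baseline definitions, which the open-label tables must label clearly.
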